Study Protocol with Statistical Analysis Plan

Study Title: Augmenting Exposure Therapy for Social Anxiety With Transcranial Direct Current Stimulation

NCT03743571

Document Date: Submitted to the IRB on March 26, 2020

Part II Application – Social Behavioral/Education Research

Note the following:

1. A Part I Cover sheet is required for each project submitted in IRBNet; see [Locating the Cover Sheet](#)
2. See IRB policy for submission requirements for new projects for [Full Committee Review](#) or [Expedited Review](#).

PI Responsibilities

1. How will the PI ensure that all study personnel are informed about the research plan and their research-related duties?	 Routine meetings  Regular communication (e.g., email, phone)  Other research staff training, describe:
--	--

Study Sites and Collaborating IRBS

2. List/describe the study sites:	UNR campus only
3. Will this research be reviewed by other IRBs?	 No  Yes (Consider contacting our office for assessment and coordination of single IRB review.)

Selection of Research Participants

4. How many participants (or records) will be enrolled?	200 Number of participants (NOTE: This is for participants enrolled in the in-person portion of the study. However, we expect that many of those who complete the online prescreen may not meet criteria for participating in the full/in-person study or may not wish to schedule in-person lab visits. We therefore expect the number of individuals who complete the online prescreen will be much higher than 200.)
5. What are the participant eligibility inclusion criteria?	

Inclusion criteria:

- 1) Age 18 or older (i.e., adult able to provide consent).
- 2) Identifies as Latino, or non-Latino and Caucasian
- 3) NOT currently receiving in exposure therapy for social anxiety.
- 4) Levels of social anxiety that are sufficiently high, defined as:
 - Reporting a 6 or higher in response to the question "How anxious would you feel giving a formal speech before a live audience?" on a 0 (no anxiety) to 8 (extreme anxiety) scale
 - Reporting a 5 or higher in response to the question "How likely would you be to avoid taking a class that required an oral presentation?" on a 0 (never avoid) to 8 (always avoid) scale

Age, specify: 18 or older

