---	---

28. State the study purpose, research hypothesis, or research questions:
	
Design: We will recruit participants with a fear of public speaking, the most commonly feared situation among individuals with social anxiety and among the general population [12-14]. Participants will be randomized to receive either active/anodal or sham tDCS stimulation targeting the vmPFC during one, 20 to 30-minute exposure therapy session delivered through virtual reality (VR). VR-based exposure therapy for public speaking anxiety is equally effective as in vivo/in life exposure therapy [8], but allows for greater consistency of the exposure environment between participants (e.g., consistency in listener facial expressions). During exposure therapy, participants will complete six, 3-minute public speaking trials. During each 3-minute public speaking trial, the audience will be comprised of either 75% Latino individuals/25% non-Latino Caucasian individuals, or 75% non-Latino Caucasian individuals/25% Latino individuals (gender of audience members will be equally distributed among each ethnicity group). Order of ethnicity matched and unmatched trials will be randomized.
 
Severity of social anxiety will be assessed at baseline and 1-month follow up with (1) a validated battery of questionnaires (the Personal Report of Public Speaking Anxiety and the Self-Statements during Public Speaking Scale), and (2) two behavioral approach tests (BATs), each involving a short speech in virtual reality to either an ethnicity matched or ethnicity unmatched audience. Fear will be assessed during each BAT behaviorally (total duration of speech out of a 5-min maximum), physiologically (electrodermal response and heart rate variability), and subjectively (peak fear rating on a scale from 0 to 100).
 
Study Aims:
 
Test the hypothesis that augmenting exposure therapy with tDCS facilitates alleviation of social anxiety symptoms. If tDCS targeting the mPFC improves treatment response, we would expect to detect lower symptom scores in the active (versus sham) tDCS group on self-report and BAT measures at 1-month follow-up. If tDCS is ineffective, we anticipate observing no differences in symptom severity between the active and sham tDCS groups at one-month follow-up.
 
Test the hypothesis that pairing exposure therapy with active (vs sham) tDCS facilitates extinction of fear response toward ethnic out-group, public speaking audiences. If tDCS facilitates reduction of fear toward ethnic out-group individuals, we expect an interaction between tDCS group (active vs. sham; between-subjects variable) and public speaking audience (ethnic-matched vs. ethnic-unmatched; within subjects variable) on behavioral, physiological, and subjective indices of fear response during the BATs at one-month follow-up. We expect that the active tDCS group will show equally low fear response on ethnic-matched and ethnic un-matched BATs at one-month follow-up, and the sham tDCS group will show higher fear responding during the ethnic un-matched BAT relative to the ethnic-matched BAT at one-month follow-up.

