30. Check all research methods/procedures that apply to this research:	
 Psychological or behavioral interventions/treatments
 
 Educational activities/interventions
 
 Experimental-control group assignment
 
 Cross-over design
 
 Computerized simulations
 
 Equipment/devices^{xi}, specify: transcranial direct current stimulation; Empatica E4, ambulatory physiological recording; HTC Vive (virtual reality)
 
 Ethnographic research
 
 Needs assessment research
 
 Program evaluation research
 
 Observational research
 
 Surveys, interviews, focus groups
 
 Collection of data from records
 
 Retrospective
 
 Prospective
 
 Other, specify:

31. Which of these methods/procedures are experimental (i.e., conducted to evaluate safety/efficacy or other outcomes) ^{xii} ?	Augmenting this exposure therapy with tDCS stimulation targeting the mPFC is experimental.
32. Which of these methods/procedures are considered standard-of-care?	Using exposure-based therapy to treat social anxiety is standard of care.
33. Who will provide the standard treatment or care referenced above?	
 N/A, research does not include usual care/standard treatment
 
 Study team
 
 Participant's own health care provider
 
 Other, specify

34. Why is group assignment necessary, and how will participants be assigned to treatment/experimental or control groups?	
 N/A, research does not involve group assignment
 
Justification/description: We will use a blocked randomization procedure and a random numbers generator to determine random assignment. Random assignment is necessary to provide an empirical evaluation of whether active/anodal tDCS improves outcomes relative to a placebo condition (sham tDCS stimulation).

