	
Before and after exposure therapy, and before and after each behavioral avoidance test (BAT), participants will additionally self-report on their emotional state (e.g., fear levels) and beliefs (e.g., belief that public speaking practices will be/were harmful/negative). During exposure therapy, participant's physiological responding will be recorded (heart rate and electrodermal skin response). After exposure therapy is complete, participants will fill out a question indicating their best guess as to their treatment assignment (placebo or active tDCS). This question is to ensure that blinding was effective.
 
Behavioral avoidance tests (BATs): Participants will be complete two behavioral avoidance tests. The BATs will involve providing two public speeches to an audience in virtual reality that is A) 75% matched to the participant's ethnicity, and b) 75% un-matched to the participant's ethnicity. Participant's responding will be measured subjectively (with self report items), physiologically (with electrodermal skin response and with heart rate), and behaviorally (recording duration eye contact with audience members, and overall duration of the speech). The subjective, physiological, and behavioral measures of anxiety during the behavioral avoidance task provide a triangulated measurement of the construct of public speaking anxiety. The behavioral approach tests will be completed at baseline and 1-month follow up.
 
Modifications to procedures due to COVID-19 restrictions: For the online follow-up survey, only the following questionnaires will be included, due to participants' completing the survey at home: Intergroup Anxiety Scale, Personal Report of Public Speaking Anxiety, Self-Statements During Public Speaking, and a modified MINI – Social Anxiety interview so that participants can answer the questions without the presence of an interviewer. See Appendix- Questionnaires to view interviews that have been modified to questionnaires.

40. How will researchers analyze the data? ^{xvi}	Primary analyses will be ANCOVAs, evaluating the impact of tDCS group (active vs sham) on outcome measures (questionnaires, physiology, and behavior) at post-treatment and follow-up, controlling for baseline levels. The hypothesis is that participants with active (vs sham) tDCS will have

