	
lower symptom scores at post-treatment and follow-up (adjusting for baseline levels).
 
We will also use a repeated-measures ANOVA to examine whether tDCS group (active vs sham; between-subjects variable) interacts with ethnic make-up of the public speaking audience (ethnicity- matched vs. ethnicity-unmatched; within-subjects variable) to determine fear response on each index of fear reactivity (behavioral, physiological, and subjective fear response) at one-month follow-up.

41. Will this research include records of participants' voices or images? ^{xvii}	
 No
 
 Yes, audio; describe and justify:
 
 Yes, video; describe and justify:
 
 Yes, photographs; describe and justify:

Research Risks	

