	
Our best estimate of other more minor symptoms comes from a recent publication. Poreisz et al., (2007) tested 102 participants in 567 tDCS sessions. In post-session questionnaires asking for ratings from 1(low) - 5 (high), a mild-tingling sensation occurred in 71% of participants and was given a mean rating of $1.74 \pm .84$. Other effects included moderate fatigue in 35% (rated 2.17 ± 1.11), itching under the electrode placement in 30% (rated $1.6 \pm .72$). More serious symptoms of burning sensations were reported in 22% (rated $1.59 \pm .91$) and pain in 16% (rated $1.41 \pm .71$). However, no participant asked to terminate a session. In our testing experience, participants describe a slight itching sensation when the stimulation begins and ends. We anticipate participants describing slight itching and tingling. If participants report burning and pain at any point during the session, we will ask them if they would like to end the testing session. If the symptoms are not resolved by ending stimulation, we will take the participant to the health center or call medical emergency services if needed. If the participant reports feeling extreme symptoms during stimulation in the 'Post-Study Questionnaire' we will speak with the participant to see if medical attention is needed.
 
3) Additionally, completing procedures such as exposure therapy and the behavioral avoidance tests, can produce an increase in anxiety; during these procedures participants are engaging in a feared task on purpose (in this study, giving a public speech). However, this risk of psychological distress does not exceed what one might experience in daily life (e.g., when asked to provide a speech/presentation in a classroom setting). To provide participants resources for additional social anxiety treatment if desired, all participants who begin treatment will be provided a referral document, listing contacts for local mental health resources, at the end of the study.
 
4) Finally, the use of immersive virtual reality (used to administer exposure therapy in our study) can occasionally lead to transient side effects such as motion sickness, dizziness, or headaches. Following procedures used by prior studies of VR-based exposure therapy for public speaking anxiety (Anderson et al., 2013), we will mitigate the risk of simulator sickness by limiting the virtual reality exposure therapy session to 20-30 minutes. Participants will be allowed to request to stop VR sessions early, or take breaks during VR sessions, as needed if they are experiencing symptoms associated with simulator sickness.
 
Anderson, P. L., Price, M., Edwards, S. M., Obasaju, M. A., Schmertz, S. K., Zimand, E., & Calamaras, M. R. (2013). Virtual reality exposure therapy for social anxiety disorder: A randomized controlled trial. Journal of Consulting and Clinical Psychology, 81(5), 751-760. http://dx.doi.org/10.1037/a0033559
 

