
44. List the discomforts and physical harms that might result from participation in this research; assess the probability, severity, and duration of each discomfort/harm:
	
1) Potential physical discomfort associated with tDCS: There is risk of seizure, skin irritation (itching, tingling, redness, pain) and burning associated with the application of electrical current to the scalp. There is risk of headache and discomfort from the adjustable bands that hold the electrodes in place. Seizure activity is associated with symptoms of attention deficiency, nausea, mood changes, and changes in perception, thus, these symptoms are also monitored. However, there have been no seizures associated with tDCS. Symptoms associated with seizure activity (nausea, mood and perceptual changes) are unlikely. The stimulus parameters we propose (1-2 mA stimulation) are consistent with what has been safely used by other researchers and because of this we think that the likelihood of a serious event is very small.
 
Our best estimate of other more minor symptoms comes from a publication on a large sample exposed to tDCS. Poreisz et al., (2007) tested 102 participants in 567 tDCS sessions. In post-session questionnaires asking for ratings from 1(low) - 5 (high), a mild-tingling sensation occurred in 71% of participants and was given a mean rating of $1.74 \pm .84$. Other effects included moderate fatigue in 35% (rated 2.17 ± 1.11), itching under the electrode placement in 30% (rated $1.6 \pm .72$). More serious symptoms of burning sensations were reported in 22% (rated $1.59 \pm .91$) and pain in 16% (rated $1.41 \pm .71$). However, no participant asked to terminate a session. In our testing experience (in the [name]/co-PI lab), participants typically describe a slight itching sensation when the stimulation begins and ends. Therefore, we anticipate participants will likely describe slight itching and tingling, but that this effect will be transient.
 
(2) Potential simulator sickness related to VR use: Probability of simulator sickness is reported by Gregg & Tarrier (2007): "In a series of experiments 80% of all participants reported an increase in sickness symptoms following immersions in a virtual environment (Cobb et al., 1999). For the majority this was a mild increase, which subsided after exiting the immersion. However, 5% could not complete the immersion because the effects were so aversive. Symptom onset typically occurred within 15 min of starting. In repeated trials, symptoms were worse during the first immersion and were negligible by the third."
 
Thus, it is likely that a participant might experience a mild, but transient, increase in simulator sickness symptoms (e.g., slight nausea, headache, etc), but rare that the increase would be so significant that a participant would need to terminate an exposure therapy session. This risk is further mitigated in the present study due to little to no movement in position during the public speaking simulation.
 

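### The Aim 2 repeated-measures ANOVA drops anyone with only one usable one-month speech; a mixed model would keep that value, though the likely gain is small

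*Combined protocol and SAP*

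**What the plan says.** Item 28 describes two virtual-reality BAT speeches at baseline and at one month, one to an ethnicity-matched and one to an unmatched audience. Fear is measured by speech duration (maximum 5 minutes), by physiology, and "subjectively (peak fear rating on a scale from 0 to 100". The Aim 2 prediction is that the active arm is equally low on both BATs while "the sham tDCS group will show higher fear responding during the ethnic un-matched BAT relative to the ethnic-matched BAT at one-month follow-up".

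Item 40 gives the analysis in one sentence: "We will also use a repeated-measures ANOVA to examine whether tDCS group (active vs sham; between-subjects variable) interacts with ethnic make-up" of the audience, separately for behavioural, physiological and subjective fear at one month. It has no rule for a participant with one of the two values.

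Randomised order is stated for the six exposure trials (items 28 and 35). No order is stated for the BATs. In the online follow-up used during campus closure (item 39), only questionnaires are collected, so both BATs are missing.

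**The concern.** With one two-level within-person factor, the interaction test is a two-sample t-test on each person's gap between the two speeches. A person with one usable value has no gap and drops out, and the speech they did give is thrown away. The documents do not say that only complete pairs are used. That is how the named method ordinarily works, and nothing in item 40 overrides it.

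Single values can arise when a wristband recording fails in one speech, or when a session ends before the second. If loss is haphazard, the cost is precision. If it depends on how the first speech went, and more people are lost in one arm, the remaining pairs are selected differently by arm and the interaction estimate can shift.

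**Working it through.** The plan gives no power calculation, SD, correlation, alpha or loss rate, so there is no figure of its own to reproduce.

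**Inputs from the documents.** 200 in-person participants (item 4); blocked randomisation with no stated ratio (item 34); two BATs at one month (items 28 and 39); a 0-100 fear scale (item 28).

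**Assumptions.** 100 per arm; two-sided 5%; correlation ρ between the two speeches of 0.4-0.6; SD 25 where points are used; true interaction zero. The interaction is the (unmatched minus matched) gap in sham minus the same gap in active, so a positive value is the predicted direction. Scores were simulated as unbounded normal.

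**1. Precision with complete data.** In SD units, SE = √(4(1−ρ)/n) with n per arm. For n = 100: ρ = 0.6 gives √0.016 = 0.13; ρ = 0.4 gives √0.024 = 0.155.

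**2. Random loss of single values.** If each recording is lost with probability q, a share 1 − (1−q)² of participants lack at least one value: 9.8% for q = 0.05 and 19% for q = 0.10. For known covariance, the complete-pair SE relative to an analysis of all values is √(1 + (1−ρ)q/(1−q)).
- q = 0.05, ρ = 0.6: √(1 + 0.4 × 0.0526) = 1.010
- q = 0.10, ρ = 0.4: √(1 + 0.6 × 0.111) = 1.033

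The loss of precision is about 1-3%.

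**3. Second speech lost after a high first score, matched audience always first.**
- *Graded loss* (probability rising smoothly with the first score, active arm 0.40 SD lower, about 10-20% of pairs incomplete). Simulations with several loss curves gave a complete-pair bias of 0.01-0.05 SD and rejection of about 5-6%. Check: rejection ≈ Φ(−1.96 + b/SE) + Φ(−1.96 − b/SE); with b = 0.05 and SE = 0.155 this is 6.2%.
- *Sharp cut-off* (everyone above a threshold is lost). Bias per arm is (1−ρ) × SD × φ(c)/Φ(c), where Φ(c) is the share retained. For loss of 20% sham and 10% active at ρ = 0.6: 0.4 × 25 × (0.350 − 0.195) = 1.55 points, or 1.55/25 = 0.06 SD. A simulation with 21% and 8% loss and a 15-point arm difference gave 2.0 points (0.08 SD) and 9.0% rejection. The mixed model gave −0.05 points and 5.5%.
- *Heavy loss* (34% sham, 16% active, sharp cut-off). ANOVA 2.8 points and 11.8%; mixed model 0.0 and 5.2%.

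**4. Order and balance of loss.** With the unmatched audience first and 34%/16% loss, the ANOVA bias is −2.8 points, against the prediction. With balanced order it is −0.1 points (4.6% rejection). With equal 21% loss in both arms, matched first, it is +0.1 points (4.8%).

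**5. Mechanisms that do not favour the mixed model.**
- *Loss driven by a person's general fear level* (8-16% incomplete). Absolute bias was at most 0.01 SD for complete pairs and 0.01-0.03 SD for the mixed model; with a steeper mechanism, 0.00 and 0.05 SD. General fear cancels in the within-person gap, which protects the complete-pair test.
- *Loss driven by the unseen second speech* (34%/16%, matched first). ANOVA −2.8 points and 11.9%; mixed model −4.7 points and 25.8%. With balanced order both were close to zero (rejection 5.4% and 5.1%).

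The mixed models simulated here contained neither baseline values nor speech order.

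**The case against.** A reader might infer several stronger things that the documents do not support.

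*That the ANOVA will manufacture the predicted interaction.* This needs a matched-first order and more loss in sham. Neither is stated; step 4 shows the sign reversing or the bias vanishing otherwise.

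*That the protocol foresees fear-driven loss.* Item 42 says "Participants will be allowed to request to stop VR sessions early, or take breaks during VR sessions", and item 44 cites a source in which "5% could not complete the immersion because the effects were so aversive". Both concern simulator sickness, and the item 42 text is about the exposure session. The same source reports negligible symptoms by the third immersion, whereas the one-month BATs are the ninth and tenth VR speeches (two baseline BATs and six trials come before). Item 44 itself calls such termination rare.

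*That stopping early means missing data.* Duration is an outcome, so a speech cut short still gives a value, and the participant can still rate peak fear. What the plan leaves open is how a refused speech is scored.

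*That the mixed model removes the problem or rests on a weaker assumption.* Step 5 shows mechanisms under which it is the more biased of the two. The two assumptions differ, and neither contains the other.

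*That the active-versus-sham difference is also distorted.* Simulated complete-pair arm effects were 6-14% too small, but item 40 tests the arm effect by ANCOVA ("Primary analyses will be ANCOVAs, evaluating the impact of tDCS group (active vs sham) on outcome measures") and uses this ANOVA for the interaction only.

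These objections limit the size and scope of the point. What stands is that the named method discards observed values and the plan has no rule for them.

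**Conclusion.** The point holds as an improvement to the analysis; it does not show that the Aim 2 result will be wrong. Under first-speech-driven loss with fixed order and roughly 10-20% incomplete pairs, the interaction bias is about 0.01-0.05 SD against an SE of about 0.13-0.16, with a false-positive rate of about 5-6%. A sharp cut-off at similar loss raises this to about 0.08 SD and 9%. Rates of 12% or more appeared only with a third or more of the sham arm losing the second speech. Random loss costs about 1-3% in SE. All of these sizes rest on assumed correlations, arm effects and loss mechanisms.

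The one systematic loss of BATs that the documents describe is the online follow-up, which removes both speeches. Neither analysis recovers those participants.

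**What to change.** In item 40, replace the Aim 2 sentence with a linear mixed model (REML) for each fear index, fitted to every available one-month BAT value. Fixed effects: tDCS group, audience, their interaction, speech order (first or second) and the baseline BAT values already collected. Use an unstructured 2 × 2 within-person covariance. Report incomplete pairs by arm and by order, and keep the complete-pair ANOVA as a sensitivity analysis.

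Two short additions make this workable. State the BAT order in item 39: if it is fixed, order cannot be separated from audience and the order term must be dropped. State how a refused or stopped speech is scored on each index, so that it is clear which values count as missing.

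The cost is a few sentences and no new data. With complete data and no order or baseline terms, the mixed model gives the same interaction test as the ANOVA; with those terms it will not match exactly, which is a further reason to report both. The mixed model is valid only if loss depends on observed values. Baseline values and order make that more plausible but do not guarantee it, so a disagreement between the two analyses should be reported as uncertainty about the interaction.

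### The tDCS-by-audience test uses one-month values only; adjusting for the baseline audience gap already collected could sharpen the same test at almost no cost

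*Combined protocol and SAP*

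**What the plan says.** Item 40 describes two analyses. The first is for the main effect of stimulation: "Primary analyses will be ANCOVAs, evaluating the impact of tDCS group (active vs sham) on outcome measures". It covers self-report, physiological and behavioral outcomes, and baseline is taken into account, since the comparison is made "at post-treatment and follow-up, controlling for baseline levels". The second is additional and addresses the audience question: "We will also use a repeated-measures ANOVA to examine whether tDCS group" interacts with the ethnic make-up of the audience, "to determine fear response on each index of fear reactivity (behavioral, physiological, and subjective fear response) at one-month follow-up". No baseline term is named for this second analysis.

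Item 28 (Study Aims) states the matching hypothesis as a group-by-audience interaction at one month. Under Design, the same item describes "two behavioral approach tests (BATs), each involving a short speech in virtual reality to either an ethnicity matched or ethnicity unmatched audience", and item 39 says "The behavioral approach tests will be completed at baseline and 1-month follow up". Assignment is by blocked randomization (item 34), and 200 people are to be enrolled in the in-person study (item 4).

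The COVID-19 modification in item 39 also bears on this test. It reads "For the online follow-up survey, only the following questionnaires will be included", and the list that follows contains no behavioral approach test (BAT).

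**The concern.** The planned test is not an error. Randomization makes the comparison of one-month values unbiased, and the time point matches the hypothesis. The point is efficiency. Each participant gives one speech to each audience type at baseline, so the quantity that the interaction is about, the unmatched-minus-matched gap, is known before treatment. The primary ANCOVAs in the same item use baseline, and this test does not.

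The stake is power for a secondary question. If people with a large gap at baseline tend also to have a large gap at one month, ignoring the baseline gap leaves explainable variation in the error term. Precision may be scarce here, since anyone followed up online has no one-month BAT. How baseline is brought in matters too: the familiar three-way version, adding time as a factor, can do worse than the present plan.

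**Working it through.** The documents give no effect size, SD, alpha, power or correlation for this test, so there is no stated figure to reproduce.

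**Inputs from the documents.** Two audience levels per person at each visit, and BATs at baseline and one month (items 28 and 39); randomized arms (item 34); 200 enrolled (item 4).

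**Assumptions.** Equal arms, so 100 per arm, with 60 per arm as a lower case; two-sided 5%; effect 0.30 SD of the one-month gap; equal gap SD at both visits; baseline BATs done before stimulation; ρ of 0, 0.2, 0.3 and 0.5.

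**Step 1: what the planned test is.** With two within-person levels, the group-by-audience F equals the squared two-sample t on the one-month gap. A simulated data set confirmed this (F = t² = 7.471).

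**Step 2: variance of the arm difference, in SD² units, with n per arm.**

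- Planned: 2/n, on 2n − 2 df.
- Adjusted for the baseline gap: (2/n)(1 − ρ²)(1 + 1/(2n − 4)), on 2n − 3 df.
- Change in gap (group by audience by time): (2/n) × 2(1 − ρ), on 2n − 2 df.

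**Step 3: one case in full, n = 100 and ρ = 0.3.**

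- Planned: variance 0.0200, SE 0.1414, noncentrality 0.30/0.1414 = 2.12, power 56.0%.
- Adjusted: variance 0.02 × 0.91 × (1 + 1/196) = 0.01829, SE 0.1353, noncentrality 2.22, power 59.8%.
- Change: variance 0.02 × 1.4 = 0.0280, SE 0.1673, noncentrality 1.79, power 43.0%.

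**Step 4: power over the range (noncentral t).**

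| n per arm | Test | ρ = 0 | ρ = 0.2 | ρ = 0.3 | ρ = 0.5 |
|---|---|---|---|---|---|
| 100 | Planned | 56.0% | 56.0% | 56.0% | 56.0% |
| 100 | Adjusted | 55.8% | 57.5% | 59.8% | 68.1% |
| 100 | Change | 32.0% | 38.6% | 43.0% | 56.0% |
| 60 | Planned | 37.1% | 37.1% | 37.1% | 37.1% |
| 60 | Adjusted | 36.8% | 38.1% | 39.8% | 46.6% |
| 60 | Change | 21.1% | 25.2% | 28.1% | 37.1% |

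The adjusted test breaks even with the planned one at ρ of about 0.07 (100 per arm) or 0.09 (60 per arm). With 100 per arm, the effect detectable with 80% power is 0.398 SD as planned, against 0.399, 0.391, 0.381 and 0.346 SD adjusted, for the four values of ρ in order.

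**Step 5: simulation checks.** With 40,000 trials per ρ at 100 per arm, planned / adjusted / change power was 55.8 / 57.4 / 39.0% at ρ 0.2, 55.7 / 59.5 / 42.7% at 0.3 and 56.0 / 68.2 / 56.2% at 0.5. A separate set of 20,000 trials per setting put type I error at 0.048 to 0.053 planned and 0.047 to 0.051 adjusted, with the same mean estimate (0.397 for both at 200 participants and ρ 0.5). The estimand does not change.

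**Step 6: what ρ means here.** It is the correlation of difference scores, not of raw BAT scores. With equal variances, ρ = (same-audience minus cross-audience correlation over time) / (1 − within-visit correlation). Illustrative values of 0.6, 0.5 and 0.7 give 0.1/0.3 = 0.33; values of 0.6, 0.6 and 0.7 give 0.

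**Step 7: adjusting for average baseline level.** A covariate uncorrelated with the gap, which is what the two-audience average is if SDs are equal and retest correlations symmetric, gave 55.6 to 56.0% against 55.7 to 56.3% planned at 100 per arm. That is no gain.

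**The case against.** The strongest reply is that nothing is broken: this is an additional analysis, valid as planned and aimed at the stated hypothesis, and the benefit rests on a correlation the documents do not contain. Difference scores often correlate weakly over time, and at ρ 0.2 the gain is only 57.5 − 56.0 = 1.5 points (100 per arm) or 38.1 − 37.1 = 1.0 point (60 per arm). That stands, and it is why the point is only a suggestion.

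The outcomes are also bounded: speech duration is capped at five minutes and peak fear runs from 0 to 100. Someone who reaches the cap in both speeches has a duration gap of zero. The normal-theory figures therefore will not fit every index equally, and ceiling effects may lower ρ. This can shrink the gain, but it does not bias the comparison between randomized arms.

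Missing one-month BATs may threaten this aim far more than a missing covariate, and adjustment does not recover them. With 60 per arm and ρ 0.3, power is below 40% either way. That also stands.

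Finally, item 28 predicts a pattern within each arm as well as an interaction, and the ANOVA shows the cell means directly. The regression alone does not, but the arm-by-audience means can be reported beside it.

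**Conclusion.** The point holds as an optional gain in precision, not as a correction of bias or type I error. On the assumptions above, the gain is negligible at ρ of 0.2 or below, modest at 0.3 (3.8 points with 100 per arm, 2.7 with 60) and material at 0.5 (12.1 and 9.5 points). The largest loss, at ρ = 0, is about 0.2 points with 100 per arm and 0.3 with 60. That asymmetry is the case for adopting it. Confidence in the size is medium, because ρ, the effect size and the number with one-month BATs are all unstated, and ρ may differ between indices.

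**What to change.** Amend item 40 so that, for each BAT index, the one-month unmatched-minus-matched difference is regressed on tDCS arm and the same difference at baseline. The arm coefficient is then the interaction test. State this before unblinding, and report the arm-by-audience means alongside it so that the within-arm pattern predicted in item 28 remains visible.

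Two substitutes should be avoided. A group-by-audience-by-time test is less powerful than the current plan when ρ is below 0.5. Adjustment only for the baseline average over audiences does not use the gap.

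Baseline BATs are planned for everyone. If one is missing, mean imputation of the covariate keeps the participant in the analysis.

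The cost is one sentence and one degree of freedom, with no new data.
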